## 1.0 Overview

### 1.1. Protocol Synopsis

Protocol Number:	5714
Protocol Title:	Assessment of Safety of Air Travel in Patients with Diffuse Cystic Lung Disease
Study Chair:	[name]
Statistician:	[name]
Consortium:	Rare Lung Diseases
Participating Sites:	University of Cincinnati
Activation Date:	December 4, 2015
Sample Size:	300 subjects - 100 with Birt-Hogg-Dubé Syndrome (BHD), 200 with Pulmonary Langerhans Cell Histiocytosis (PLCH)
Target Enrollment Period:	September 2015 – September 2016
Study Design:	This is a questionnaire-based study of patients with diffuse cystic lung diseases (DCLDs) to gather information relevant to safety of air travel, especially pertaining to the risk of pneumothorax associated with air travel. In addition, this study will be used to further characterize clinical aspects of disease and establish a contact registry for patients.
Primary Study Objective(s):	To define the risk of pneumothorax associated with air travel in patients with DCLD.
Secondary Study Objective(s):	

• To establish a contact registry for patients with BHD and PLCH

• To define the clinical phenotype of each DCLD in their respective cohort of patients

• To define current screening practices for surveillance of disease-specific anomalies (i.e. renal tumors in BHD)

	
The study will enroll participants through the clinic network at the Rare Lung Disease Consortium (RLDC) and through the BHD and PLCH foundation websites. Participants will have access to the questionnaire via REDCap (an online data management system) and each participant will be provided a link to complete the survey. In case of lack of internet access or inability to complete the online questionnaire, a paper survey will be mailed out with a pre-paid envelope to return the survey.
 
Inclusion Criteria:
 

• Adult, age 18 or older

• English literate

• Signed, dated informed consent; either given electronically or via paper form

• Diagnosis of BHD, or PLCH as defined by accepted clinical, histopathological and/or genetic criteria.

➢ For BHD, diagnosis would include the presence of fibrofolliculomas/trichodiscomas on skin biopsy, or the presence of pathogenic FLCN mutations.

➢ For PLCH, it would include characteristic radiographic findings and tissue biopsy consistent with PLCH (presence of CD1a positive Langerhans cells or stellate fibrosis in late stages).

 
Exclusion Criteria:
 

• Inability to give informed consent

Outcome Measures:	Number of pneumothoraces associated with air travel, estimated as a percentage of the number of flights taken.
Statistical Considerations (sample size and analysis plan):	Data from all surveys will be pooled together. The rate of pneumothorax will be estimated as a percentage of the number of flights taken. We will compare other disease and patient characteristics to try to determine factors associated with an increased risk of in-flight pneumothorax.
Variables collected	
 
• Contact information
 
• Demographics
 
• Age, gender, ethnicity
 
• Medical history
 
• Diagnosis
 
• Surveillance information for associated clinical anomalies, such as renal tumors in BHD
 
• Evaluation of dyspnea, other pulmonary problems and need for supplemental oxygen
 
• Family history
 
• Smoking history
 
• Pneumothorax information (diagnosis, management, measures to prevent prevention such as pleurodesis, relationship with flights)
 
• Flight history
 
• Effect of pneumothoraces on attitudes towards undertaking air travel
 

Ethical and Scientific Review Procedures	Institutional Review Board approval will be obtained. Informed consent will be obtained from participants. Every effort will be made to protect participant confidentiality according to privacy laws and medical record confidentiality regulations.
Data Ownership	[name].
Sponsors (federal, state, foundation and industry support):	National Institutes of Health (NIH) U54

## **1.2. Lay Summary**

Birt-Hogg-Dubé syndrome (BHD) is an uncommon genetic disease characterized by tumors in the hair follicles and kidneys, as well as lung cyst formation. These lung cysts can rupture thus placing patients with BHD at a higher risk for development of pneumothoraces, or collapsed lungs.

Pulmonary Langerhans cell histiocytosis (PLCH) is an uncommon disease characterized by the formation of cysts in the lungs, and is strongly associated with smoking cigarettes. Similar to BHD, patients with PLCH have an increased risk of development of pneumothoraces.

The safety of air travel in patients with BHD and PLCH is not established. The concern with air travel in these diseases is related to the risk of cyst expansion with decreasing atmospheric pressure, which could lead to cyst rupture causing a pneumothorax. Safety of air travel has been studied for patients with lymphangioleiomyomatosis (LAM), another rare cystic lung disease. Based on the results from studies done in patients with LAM, recommendations regarding air travel are provided to patients with BHD and PLCH. The aim of this study is to conduct a survey-based assessment of patients with BHD and PLCH and establish the risk of pneumothorax associated with air travel in these diseases.

As a follow up to the original protocol, we plan to re-contact all patients who gave us permission in the survey to contact them again. We will obtain results of their lung function tests and images of CT chest to correlate PFT data and cyst preponderance (size, number, volume etc.) with the risk for spontaneous pneumothorax.

## **1.3. Detailed Description**

The aim of this study is to conduct survey-based assessments for the safety of air travel in patients with BHD and PLCH. The study will enroll patients through the clinic network at Rare Lung Disease Consortium (RLDC) and through the BHD and PLCH foundation websites. Patients will have access to the questionnaire via REDCap (an online data management system) and each patient will be provided with a link to complete the survey. In case of lack of Internet access or inability to complete the online questionnaire, a paper survey will be mailed out with a pre-paid and addressed envelope to return the survey. Paper surveys returned to [name] [name] will be entered into REDCap by the clinical research coordinator. We plan on enrolling approximately 100 patients with BHD and 200 patients with PLCH for the purpose of this study. Secondary aims of this study include further characterization of the clinical aspects of disease and to establish a contact registry for these patients, in order to facilitate future studies.

This research will be accomplished as part of the Rare Lung Disease Clinical Network Consortium, with data stored and analyzed by the Data Management and Coordinating Center (DMCC) at the University of South Florida as part of the NIH-supported Rare Disease Consortium.

## **2.0 Specific Aims (Hypothesis and Objectives)**

### **2.1. Hypothesis**

The hypothesis to be tested is that air travel is safe in patients with diffuse cystic lung diseases, and there is no increased risk of pneumothorax in this disease population related to air travel.

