## **6.0 Statistical Considerations**

Data from all surveys will be pooled together. The rate of pneumothorax will be estimated as a percentage of the number of flights taken. We will compare other disease and patient characteristics to try to determine factors associated with an increased risk of in-flight pneumothorax. All analyses will be done by using SAS for Windows, version 9.4, Cary, NC.

NIH Approved 02-28-17

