Assessment of Safety of Air Travel in Patients with Birt-Hogg-Dube Syndrome

NCT03040115

Statistical analysis plan

Document date: August 5, 2015

The rate of pneumothorax will be estimated as a percentage of the number of flights taken. Because retrospective distinction between persistent and recurrent pneumothorax can be problematic, all ipsilateral pneumothoraces reported within the same month will be considered as one episode. If a given pneumothorax was treated with more than one intervention (e.g., chest tube followed by chemical pleurodesis followed by surgical pleurodesis), the most aggressive intervention (e.g., in this case, surgical pleurodesis) will be listed as the treatment of record for that event. For the purpose of our study, a pneumothorax that happened either during an air flight or within 24 hours after a flight will be defined as flight-related pneumothorax. We will compare other disease and patient characteristics to try to determine factors associated with an increased risk of in-flight pneumothorax. Statistical significance will be set at P value of 0.05 and determined by the chi-square test and the z-statistic, as appropriate. All analyses will be done by using SAS for Windows, version 9.4, Cary, NC.

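### Section 2.1 sets out to test that air travel brings no increased risk of pneumothorax, but the only planned primary statistic is a one-group percentage per flight with nothing to compare it with

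*Protocol*

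**What the plan says.** Protocol Section 2.1 states a hypothesis to be tested: that air travel is safe in these diseases and "there is no increased risk of pneumothorax in this disease population related to air travel". It does not say what the risk would be increased over.

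The primary objective in the synopsis is descriptive: "To define the risk of pneumothorax associated with air travel in patients with DCLD". The outcome measure is "Number of pneumothoraces associated with air travel, estimated as a percentage of the number of flights taken". Section 6.0 repeats this as the analysis: "The rate of pneumothorax will be estimated as a percentage of the number of flights taken". The SAP uses the same sentence and defines the numerator: "a pneumothorax that happened either during an air flight or within 24 hours after a flight will be defined as flight-related pneumothorax".

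The only comparison described is between kinds of patient: "We will compare other disease and patient characteristics to try to determine factors associated with an increased risk of in-flight pneumothorax". The next sentence of the SAP gives the tests: "Statistical significance will be set at P value of 0.05 and determined by the chi-square test and the z-statistic, as appropriate". Section 3.0 quotes background pneumothorax figures for both diseases, but no analysis uses them.

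**The concern.** A claim of no increased risk is comparative. It needs the pneumothorax rate in time linked to flights and the rate in other time, or a reference value in place of the latter. A percentage of flights supplies only the first.

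The numerator makes this matter more. It is defined by timing: any pneumothorax during a flight or in the following 24 hours counts. These patients have pneumothoraces without flying, so some events will fall in the window by chance. The percentage cannot separate those from events that flying caused.

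Sections 3.0 and 8.3 say the results are meant to help patients decide about flying and to inform recommendations. As an absolute risk, the percentage serves that use. It does not answer 2.1, because a low percentage must still be set against a background the plan does not estimate. Nothing in the documents says a low figure would be reported as proof of no increase, but 2.1 as worded invites that reading.

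**Working it through.** **The text.** The plan gives no figure to reproduce for this hypothesis. The sample size is 100 BHD + 200 PLCH = 300, with no power, margin, expected flights or expected events behind it. What the hypothesis needs, set against what is planned:

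| Needed to test no increased risk | Outcome measure (synopsis) | Protocol 6.0 | SAP |
|---|---|---|---|
| Rate per flight | yes | yes | yes |
| Rate in non-flight time, or a reference value | no | no | no |
| Margin for no increase | no | no | no |
| Confidence interval | no | no | no |
| Test with a stated null value or flight versus non-flight contrast | no | no | no (tests named, contrast not) |

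**Size, as an illustration for PLCH.** The documents give no absolute rate for BHD.

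Inputs from the documents: 200 PLCH patients (synopsis); about 15% lifetime pneumothorax and about 60% recurrence (Section 3.0); 24 hours after a flight (SAP, which is titled for BHD).

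Assumed: 3-hour flights, so a 27-hour window; 20 flights per patient, so 200 × 20 = 4,000 flights; all episodes spread over 20 to 40 years.

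1. *Episodes per patient.* With one recurrence at most, 0.15 × 1.6 = 0.24. With 60% recurrence after every episode, 0.15 / (1 − 0.6) = 0.375. A negative binomial model with 85% having none, and 60% of the rest having two or more, gives a mean of 0.515. The range used is 0.24 to 0.515; its upper end rests on that model.
2. *Per patient-year.* 0.24 / 40 = 0.0060, to 0.515 / 20 = 0.0257.
3. *Chance rate per flight.* Yearly rate × 27 / 8,766 hours = 0.00185% to 0.00793%. In 4,000 flights that is 0.07 to 0.32 expected events.
4. *Zero events, per flight.* Exact two-sided 95% upper limit: 1 − 0.025^(1/4000) = 0.0922%. Ratio to chance: 11.6 to 49.9.
5. *Zero events, per patient.* 1 − 0.025^(1/200) = 1.83% of patients. Chance over 20 flights is 0.037% to 0.159%, so the ratio is 11.5 to 49.4. This bound does not need flights within a patient to be independent.
6. *Background at which zero events in 4,000 flights would exclude a doubling.* 0.000922 × (8,766 / 27) / 2 = 0.150 episodes per patient-year, against 0.006 to 0.026 in step 2.

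**Sensitivity of the per-flight ratio with zero events**

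| Assumption changed | Upper limit per flight | Multiple of chance |
|---|---|---|
| 5 flights per patient (1,000) | 0.368% | 46 to 199 |
| 20 flights per patient (4,000) | 0.092% | 12 to 50 |
| 50 flights per patient (10,000) | 0.037% | 4.7 to 20 |
| 4,000 flights, all flights and episodes within 5 years | 0.092% | 2.9 to 6.2 |
| 10,000 flights, all flights and episodes within 5 years | 0.037% | 1.2 to 2.5 |

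For BHD (100 × 20 = 2,000 flights), only the limits can be given: 0.184% per flight and 3.62% of patients. A doubling would be excluded only at a background of 0.30 episodes per patient-year or more.

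**The case against.** **The study is descriptive.** The objectives and outcome measure ask for an estimate, and no sample size or decision rule rests on the sentence in 2.1. This stands, and it limits the point to the hypothesis. But 2.1 does not say describe; it names a hypothesis to be tested, and the two have to be reconciled.

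**The SAP does name tests at 0.05.** Nothing expressly confines the chi-square test and z-statistic to the risk-factor comparison; that reading comes from the order of the sentences. The survey also collects pneumothorax and flight history (Section 4.6), so a comparison may be possible. It is still not specified: the flight rate has no null value and no second group. A non-significant result without a margin or interval would not show the absence of an increase in any case.

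**The multiples rest on assumptions and partly measure imprecision.** This is fair. Years at risk, flight length, flights per patient and the recurrence model are all assumed, and the ratios run from 1.2 to 199. In the most favourable case, 50 flights each with all flights and episodes inside five years, zero events could exclude a doubling at the upper end of the background range. Even there the conclusion needs a background rate, which the plan does not provide. More flights would narrow the limit without supplying a comparator.

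**Conclusion.** The concern holds. No specified analysis can test the hypothesis in 2.1, for either disease: the SAP is titled for BHD, but Protocol 6.0, which pools all surveys, has the same gap. This conclusion rests on the text alone.

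The size is illustrative and for PLCH only. Under the central assumptions, even the most reassuring result, zero events, would leave room for a rate about 12 to 50 times chance. That range moves widely with flights per patient and the length of the risk period. The per-flight percentage remains a sound answer to the descriptive objective. What should change is the hypothesis and the conclusion drawn from it.

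**What to change.** 1. **Reword 2.1 as estimation.** For example: *The study will estimate the absolute risk of flight-related pneumothorax per flight, with a 95% confidence interval; it does not test whether this exceeds the background risk.* Draw no conclusion of no increased risk from the percentage alone. Cost: one sentence, and a more cautious safety statement.

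2. **Report the percentage with a 95% interval** that allows for repeated flights and recurrent episodes within a patient, by a patient-level bootstrap or a cluster-robust method. A bootstrap fails with few or no events, so in that case give the exact bound on the proportion of patients with at least one flight-related event. Cost: a small change in analysis and a wider interval.

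3. **Optional: compare flight with non-flight time.** If the survey gives usable counts of flights, at-risk years and all episodes, compare the episode rate in flight windows (overlaps merged where dates allow) with the rate in each patient's other at-risk time. Report a rate ratio with an interval clustered by patient. The questionnaire is not in the documents, so feasibility must be checked, and flight duration would have to be assumed. State the limits: recall bias, uneven hazard over time, less flying after an event, different flight frequency between patients, and the SAP rule that "all ipsilateral pneumothoraces reported within the same month will be considered as one episode".

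A statement of no increased risk should be made only against a margin fixed before the data are seen. Section 4.7 scheduled the survey analysis for January 2016, before the protocol version approved on 02-28-17, so a margin set now may come too late. If the data have been analysed, label item 3 exploratory. None of the three items needs new patients.

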### **2.2. Objectives**

1. To define the risk of pneumothorax related to air travel in patients with BHD and PLCH.
2. To establish a contact registry for patients with BHD and PLCH, in order to facilitate participation in future trials.
3. To describe the demographic and clinical characteristics of patients with BHD and PLCH, as well as ascertain clinical practices related to management and surveillance of related medical conditions, such as surveillance of renal tumors in patients with BHD.
4. To determine the relationship between lung function, and radiographic cyst characteristics and the risk of spontaneous pneumothorax in patients with BHD and PLCH.

### **3.0 Background**

BHD is a rare, autosomal dominantly inherited genodermatosis characterized by the formation of hair follicle tumors, kidney tumors, and pulmonary cysts. Pulmonary cysts are seen in 80-100% of patients with BHD, and lead to an increased risk of development of pneumothorax in these patients. Zbar et al., have reported that the risk of development of pneumothorax is 32-fold higher in patients with BHD as compared to the general population.

Atmospheric pressure changes have the potential to cause cyst expansion leading to an increased chance of cyst rupture causing a pneumothorax. Based on this risk, patients with BHD are advised to not undertake scuba diving, although no disease specific data exists for this recommendation. In general, air travel is considered to be safe in patients with diffuse cystic lung diseases, although disease specific data for safety of air travel in BHD are lacking.

PLCH is a rare diffuse cystic lung disease seen most commonly in young-middle aged adults, and is associated with exposure to cigarette smoke in greater than 90% of patients.

Approximately 15% of patients with PLCH develop a pneumothorax over their lifetime, with a recurrence rate of approximately 60% after a sentinel event. Similar to BHD, recommendations regarding air travel are given to patients with PLCH on the basis of extrapolation from other diseases.

Having specific information about safety of air travel in BHD and PLCH will help these patients make informed decisions about air travel. We aim to conduct a questionnaire-based assessment of patients with BHD and PLCH to ascertain the risk of pneumothorax related to air travel. In the first part of this study we will distribute the questionnaires for BHD, followed later by the PLCH survey. In addition, we aim to establish a contact registry for these patients in order to answer future clinical questions.

With the current amendment, we will re-contact patients with BHD and PLCH, who gave us the permission to contact them in future for other projects. We will ask permission to obtain their medical records, specifically their pulmonary function tests (PFTs), and CT scan(s) of the chest. We will correlate the PFT data and cyst features such as cyst number, size, and volume with the risk of spontaneous pneumothorax. These results will provide us the ability to do individual, patient-specific risk stratification for spontaneous pneumothorax in patients with BHD and PLCH.

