### 4.2. Inclusion Criteria

- Adult, age 18 or older
- English literate
- Signed, dated informed consent; either given electronically or via paper form;
- Diagnosis of BHD, or PLCH as defined by accepted clinical, histopathological and/or genetic criteria
  - *For BHD, diagnosis would include the presence of fibrofolliculomas/trichodiscomas on skin biopsy, or the presence of pathogenic FLCN mutations.*
  - *For PLCH, diagnosis would include characteristic radiographic findings and tissue biopsy consistent with PLCH (presence of CD1a positive Langerhans cells or stellate fibrosis in late stages).*

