### 4.5. Participant Retention

This study does not require follow-up after completion of the survey, however participants may be contacted in the future to verify and update the contact information they provided for the registry.

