### 4.6. Data Elements

Data elements for this study include the following information about study participants:

- Contact information
- Demographics
- Age, gender, ethnicity
- Medical history
- Patient reported elements of diagnostic criteria and other clinical manifestations
- Surveillance information for associated clinical anomalies, such as renal tumors in BHD
- Evaluation of dyspnea, other pulmonary problems and need for supplemental oxygen

- Family history
- Smoking history
- Pneumothorax information (diagnosis, management, measures to prevent prevention such as pleurodesis, relationship with flights)
- Flight history
- Effect of pneumothoraces on attitudes towards undertaking air travel
- Pulmonary function tests
- CT scans

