#### **4.7. Schedule of Events**

September 2015: Distribute links and paper copies of the questionnaires

November 2015: Resend links and surveys to increase recruitment

January 2016: Data Analysis

April 2016: Manuscript submission

April 2017: Contact patients and start obtaining medical records

November 2017: Data Analysis

April 2018: Manuscript submission

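### Objective 4 specifies no age adjustment or time at risk, so a lung-function or cyst feature that merely tracks age can look like a marker of pneumothorax risk

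*Protocol*

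**What the plan says.** Protocol Section 2.2 gives the fourth objective as "To determine the relationship between lung function, and radiographic cyst characteristics and the risk of spontaneous pneumothorax in patients with BHD and PLCH". The method appears in one sentence of Section 3.0: "We will correlate the PFT data and cyst features such as cyst number, size, and volume with the risk of spontaneous pneumothorax". The same paragraph states the intended use: "These results will provide us the ability to do individual, patient-specific risk stratification for spontaneous pneumothorax in patients with BHD and PLCH".

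No analysis is attached to this objective elsewhere. Protocol Section 6.0 covers the per-flight rate and a comparison of factors for in-flight events. The SAP is dated August 5, 2015, before Amendment 1 (02-23-17), and is titled for BHD only. It sets significance at 0.05 and names the chi-square test and the z-statistic.

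Four design features determine what the outcome is:

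- Entry (Section 4.2) is "Adult, age 18 or older", with no upper limit.
- The survey collects "Pneumothorax information (diagnosis, management, measures to prevent prevention such as pleurodesis, relationship with flights" (Section 4.6), with no look-back window stated.
- Section 4.5 says "This study does not require follow-up after completion of the survey".
- The schedule in Section 4.7 has "April 2017: Contact patients and start obtaining medical records". It does not say how the scan or lung-function date should relate to the event.

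Age and smoking history are collected (Section 4.6), but neither is given a role in the analysis.

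**The concern.** A retrospective history with no window and no later follow-up amounts to whether a pneumothorax ever occurred before the survey. That probability rises with years lived even when every patient has the same underlying risk. A 25-year-old without an event has had little time at risk; a 65-year-old has had decades. Any measure that changes with age, upward or downward, picks up this gradient in a crude comparison.

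The stated use makes this matter. If results are to stratify individual patients, a marker that only reflects years lived would label a young patient with few cysts as low risk merely because little time has passed. This is separate from whether the CT came before or after the event. It would remain if every scan had preceded the pneumothorax.

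**Working it through.** The plan gives no power or error-rate figure for Objective 4, so there is nothing to reproduce. The check asks how often a feature with no effect would be declared significant.

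**From the documents:** significance level 0.05 (SAP; two-sided assumed); planned numbers of 100 BHD and 200 PLCH (Synopsis); about 15% of PLCH patients ever having a pneumothorax (Section 3.0); age 18 or older.

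**Assumed:** age uniform on 18-75; correlation ρ between feature and age; prevalence up to 40% for BHD; three patterns of risk over age.

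**Model.** P(ever by age A) = 1 − exp(−λT). T is A − 15 (constant risk from 15), A (constant from birth), or min(A, 40) − 15 (no new risk after 40). λ is set so that average prevalence matches the target. The feature is x = ρz + √(1 − ρ²)ε, where z is standardised age and ε is independent noise, so x has no effect of its own.

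**Age gradient alone, 15% prevalence:**

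- Constant risk from 15, λ = 0.00528: 1 − exp(−0.0528) = 5.1% at 25; 1 − exp(−0.158) = 14.6% at 45; 1 − exp(−0.264) = 23.2% at 65.
- No new risk after 40, λ = 0.00790: 7.6% at 25, 17.9% at both 45 and 65.

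**False-positive rate of a logistic Wald test, 2,000 simulated studies per setting:**

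| N, prevalence | Risk pattern | Crude, ρ=0.3 | Crude, ρ=0.5 | Age-adjusted (ρ=0.3; 0.5) |
|---|---|---|---|---|
| 200, 15% | constant from 15 | 13.5% | 30.6% | 4.5%; 5.7% |
| 200, 15% | constant from birth | 8.7% | 16.3% | 5.1%; 4.9% |
| 200, 15% | none after 40 | 6.6% | 10.7% | 4.6%; 4.3% |
| 100, 40% | constant from 15 | 15.5% | 39.2% | 4.2%; 4.2% |
| 100, 40% | none after 40 | 8.3% | 14.3% | 5.1%; 5.3% |
| 100, 15% | constant from 15 | 9.2% | 17.5% | 5.2%; 5.2% |
| 100, 15% | none after 40 | 5.2% | 6.1% | 4.5%; 4.8% |
| 50, 40% | constant from 15 | 10.2% | 20.9% | 4.3%; 4.7% |
| 50, 40% | none after 40 | 6.2% | 9.3% | 4.1%; 4.8% |

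The simulation standard error near 5% is √(0.05 × 0.95 / 2000) = 0.5 percentage points, so 5.2% and 6.1% are close to nominal. With ρ = 0 the crude test gives 3.6-5.2%, which confirms that the excess comes from age. A chi-square test on the feature split at its median, nearer to what the SAP names, gives 5.2-12.7% at ρ=0.3 and 7.1-30.5% at ρ=0.5 across all settings run.

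A further set of runs crossed prevalence 15-40%, ρ 0.3-0.5, and constant risk or none after 40. The crude rates were about 6-29% at N=60, 6-42% at N=100 and 7-72% at N=200, against 3-6% with age in the model. The 72% is a corner case. It pairs the PLCH sample size with 40% prevalence, whereas at the protocol's own 15% the constant-risk-from-15 figures for N=200 are 13.5-30.6%.

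**The case against.** The strongest reply is that the plan is silent rather than wrong. One sentence in the Background is not an analysis specification. Age is collected, and nothing excludes adjusting for it. A reader might infer that the sponsor chose a crude analysis; the documents do not support that. What stands is that no adjustment or time at risk is specified, and that the only tests named are unadjusted.

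A reader might also take "develop a pneumothorax over their lifetime" in Section 3.0 as defining the outcome. It does not: it is background from a cited PLCH study. That the outcome is history to date is an inference from Sections 4.2, 4.5 and 4.6.

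The size is also open to challenge. The documents give neither the age-feature correlation nor the age pattern of risk, and Section 3.0 places PLCH mostly in young to middle-aged adults. If risk stops in mid-life and the correlation is weak, the bias is negligible. The analysed set is limited to those who allow re-contact and release their records; its size is not stated, and fewer patients mean a smaller excess. These points stand and are the reason for giving a range.

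Two further inferences are tempting but weak. Smoking cannot be assumed to act as age does: Section 3.0 reports smoke exposure in more than 90% of PLCH patients, so ever-smoking hardly varies, and only amount or duration could confound. Nor does the protocol say that raw rather than percent-predicted lung function will be used.

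**Conclusion.** The concern holds as an omission. If the plan is followed with only what it states, years at risk are mixed with any effect of lung function or cysts. The consequence runs from negligible to serious: roughly nominal with weak age correlation and no risk after 40, and several times nominal with ρ = 0.5 and risk continuing through adulthood. No single figure within that range can be defended from the documents. The remedy is less dependent on assumptions, since adding age returned the error rate to 3-6% throughout.

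It should be fixed before Objective 4 is analysed, because the result is meant for individual risk stratification. The primary air-travel objective is unaffected. Age adjustment does not settle whether the CT or lung-function test preceded the event or its treatment.

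**What to change.** Objective 4 needs an SAP section in any case. Suggested wording:

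*For each lung-function measure (percent predicted) and each cyst feature, the association with ever having had a pneumothorax will be estimated separately in BHD and PLCH by logistic regression adjusted for age at survey. A penalised fit will be used if events are few. In PLCH, smoking amount or duration will be added if the number of events allows.*

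A model of first pneumothorax with age as the time scale should be secondary only. It should be limited to patients with a known onset age and should state how the timing of the CT or lung-function test relative to the event is handled. A Cox model of this kind held its false-positive rate at 4.0-5.9% in simulation. However, if a scan taken after the event is entered as a fixed covariate, the hazard ratio is not that of a baseline marker.

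The cost is a few sentences, a little analysis work and one or two degrees of freedom. Age, diagnosis, smoking history and pneumothorax history are already collected. Whether the smoking item records amount or duration should be checked against the questionnaire.
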